5.7 GCSI

Gastroparesis Cardinal Symptom Index (GCSI) questionnaire will be administered at Visits 1 and 4. GCSI contains 3 subscales: post-prandial fullness/early satiety (questions 4-7), nausea/vomiting (questions 1-3) and bloating (questions 8-9).

Total scores will be calculated for the entire questionnaire and each subscale. If at least one question is not answered then the total score and the affected subscale score will not be calculated.

Individual question scores, total score and subscale total scores as well as their changes from baseline will be summarized descriptively by visit and treatment group as well as for both treatment groups combined.

All results will be listed.

5.8 Concomitant Medications

Concomitant medications are defined as medications taken while a subject took the open-label study drug, i.e. medications with stop date on or after the date of the first administration of the open-label study drug or those that are ongoing.

Concomitant medications will be coded using WHO Drug Dictionary version March 2019.

Use of concomitant medications will be summarized by ATC class (the highest available level), preferred name and treatment group, as well as for both treatment groups combined. A subject reporting the same medication more than once will be counted only once for that medication name; similarly, a subject reporting several medications in an ATC class will be counted once for that class. The summary will be ordered alphabetically by ATC class and preferred name.

Concomitant medications will also be grouped into various anti-PD medication classes:

- Amantadine

- selective MAO-B inhibitors
- anticholinergic PD medications
- dopamine agonists
- others

as well as antidepressants, sleep aids, and others.

Frequencies and percentages of subjects taking these classes of medications as well as each medication preferred name under the class will be summarized by treatment group as well as for both treatment groups combined.

All concomitant medications will be listed.

6 COVID-19 considerations for analyses

As the study will be partly conducted during the COVID-19 pandemic, a number of visits can be delayed, canceled or conducted remotely. To account for these circumstances the following changes were implemented in analysis:

1. All measurements for the following scales that were done remotely due to COVID-19 will be included in the analysis as if they were done at a face-to-face visit:
 - C-SSRS (Columbia Suicide Severity Rating Scale)
 - NMSS (Non-Motor Symptom Assessment Scale for Parkinson's Disease)
 - PAS (Parkinson Anxiety Scale)
 - PDQ-39 (39-item Parkinson Disease Questionnaire)
 - PDSS-2 (Parkinson's Disease Sleep Scale-2)
 - PGI-S (Patient Global Impression of Severity)
 - GCSI (Gastroparesis Cardinal Symptom Index)
 - TSA (treatment Satisfaction Assessment)
 - ZBI-12 (12-item Zarit Burden Interview)
 - EMSQ (Early Morning Symptoms Questionnaire)
 - MDS-UPDRS parts I, II, and IV
2. Remote measurements, due to COVID-19, of the following scales will be excluded from all analyses:
 - MDS-UPDRS Part III
 - CGI-S (Clinical Global Impression of Severity)
3. Samples for laboratory tests and ECG that were done outside of regular visits, due to COVID-19, will be included in the analysis and mapped to the closest protocol defined visit ([section 2.3](#)).
4. Subjects who discontinued for reasons related to COVID-19 pandemic will be summarized separately in the disposition tables ([section x](#))
5. Adverse events in subjects with COVID-19 will be summarized separately ([section 5.1](#))

6. Protocol deviations related to COVID-19 will be identified in the listing ([section 3.4](#))

7 Changes From Protocol-Specified Analyses

The protocol envisioned summarizing AEs, vital signs and ECG across the entire IPX203 exposure including information from the open-label extension and the prior IPX203-B16-02 study into which the subjects were enrolled. It was decided to postpone such analyses until an Integrated Summary of Safety (ISS) is prepared. Such analyses will not be done as part of this SAP.

Changes related to the COVID-19 pandemic are summarized in [section 6](#).

There are no other deviations from the protocol-specified safety analyses.

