8.4. Visit 4 – Study Completion (Month 9) or Early Discontinuation

8.4.1. Prior to Visit 4

Call the subjects prior to Visit 4 and remind them to bring any unused study medication and empty medication bottles to the visit.

8.4.2. At Visit 4

- Collect unused study drug and empty bottles.
- Review study drug accountability.

- Update IPX203 regimen (dose, frequency, number of capsules) and other concomitant medications.
- Assess vital signs after subject is supine for at least 5 minutes (blood pressure, heart rate, temperature and respiratory rate) and then assess orthostatic blood pressure and heart rate after subject is standing for approximately 2 minutes.
- Record AEs.
- Weigh the subject.
- Perform physical exam including weight.
- Perform a 12-lead ECG.
- Administer C-SSRS ([Appendix B](#)).
- Collect blood and urine samples for clinical laboratory studies ([Appendix C](#)).
- Administer MDS-UPDRS Parts I through IV ([Appendix D](#)).
- Determine PGI-S and CGI-S scores ([Appendix E](#) and [Appendix F](#), respectively).
- Complete PDQ-39 ([Appendix G](#)).
- Complete GCSI ([Appendix H](#)).
- Perform NMSS ([Appendix I](#)).
- Complete the PDSS-2 ([Appendix J](#)).
- Complete PAS ([Appendix K](#)).
- Complete the TSA ([Appendix L](#)).
- Complete the ZBI-12 ([Appendix M](#)).
- Administer the EMSQ ([Appendix N](#)).
- Contact IWRS to report subject disposition.

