9.2. Concomitant Medications

9.2.1. Permitted PD Medications and Surgical Treatments

Concomitant therapy with amantadine, selective monoamine oxidase (MAO) type B inhibitors (eg, safinamide, selegiline, rasagiline), anticholinergic PD medications (eg, benztrapine, trihexyphenidyl), hypnotics (including low doses of quetiapine ≤ 25 mg per day), dopamine agonists, including apomorphine, supplemental CD, and COMT inhibitors are allowed provided the doses and regimens (and any adjustments) are recorded on the concomitant medication form. Implantation of a deep brain stimulator (DBS) for the treatment of PD is permitted during this study provided the stimulation settings are recorded.

Although apomorphine, supplemental CD, COMT inhibitors, and DBS were not permitted in Study IPX203-B16-02, these treatments may be initiated during the current study.

All concomitant medications taken during this study will be recorded.

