2.1 Definitions of Baseline

Baseline is defined as the last assessment obtained prior to the first dose of the open-label drug in the study IPX203-B16-03.

The study eCRF does not explicitly capture when the subject took the first open-label study drug dose. It will be assumed that this dose is taken on the day of Visit 1 after all study assessments.

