3.3 Study Drug Exposure

Overall summary of study drug exposure will include descriptive summary by treatment group of the following parameters:

- Average total daily dose of IPX203 – defined as the total IPX203 dose taken over the course of the study divided by the treatment duration in days
- Average daily dosing frequency – defined as the total number of administrations over the course of the study divided by the treatment duration in days
- Treatment duration – defined as [the date of last dose] – [the date of first dose] + 1.

IPX203 dosing regimen will be recorded at each visit. Frequency of daily dose administration (number of administrations per day), total daily dose of IPX203 (in mg) and most frequently used dose (mg) and their changes from the starting (Visit 1) regimen will be summarized by visit and treatment group. If more than one dose is used most frequently, the higher dose will be selected as the most frequent dose.

Total daily dose will also be summarized categorically, categorized as < 400 , 400 to < 1000 , 1000 to < 1400 , 1400 to < 1800 , 1800 to ≤ 2400 , and > 2400 mg.

Changes in total daily dose and daily dosing frequency will be analyzed for the following time periods: Visit 1 to Visit 2, Visit 2 to Visit 3, Visit 3 to Visit 4, Visit 1 to Visit 3 and Visit 1 to Visit 4. For each period subjects will be categorized into one of the following categories:

- No change in total daily dose
- Total daily dose modified, but returned to the same level (e.g. an increase followed by a decrease by the same value)
- Total daily dose increased during the period
- Total daily dose decreased during the period

Separately subjects' changes in daily dosing frequency will be categorized in a similar way.

Number and percentage of subjects in each of these categories will be presented for each time period.

Similar comparison of both total daily dose and daily dosing frequency will be made for the subject's stable IPX203 regimen in study IPX203-B16-03 vs. the starting (Visit 1) regimen in this study.

For subjects who changed their total dose or number of daily doses the number of steps during the time period will be categorized as 1, 2, 3, 4 or >4 and also be summarized.

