5.1 Adverse Events

Adverse Events will be coded using the Medical Dictionary of Regulatory Activities (MedDRA) version 22.0 AE coding system for purposes of summarization.

Only Treatment Emergent Adverse Events (TEAE) will be used for the summary analysis, unless otherwise specified. An AE will be considered as treatment-emergent if the date of onset is on or after the date of the first open-label study drug administration in the study IPX203-B16-03 and no later than 1 day after the last study drug dose in the study. AEs with unknown start dates will be counted as treatment-emergent unless the AE resolution date is prior to the first open-label study drug administration date. If the AE start date is partially missing, the AE will be considered treatment-emergent, unless the month and year (when available) rule out the possibility that the event occurred post start of the open-label study drug and no later than 1 day after the last study drug dose.

A TEAE is defined as treatment-related if it is recorded as “possibly related” or “related” to the study medication on the eCRF. AEs recorded as “not related” or “unlikely related” will be considered not related. In case the relatedness was not assessed, the most conservative result (related) will be chosen for the analysis.

In summaries of TEAEs a subject experiencing the same AE (with the same preferred term) multiple times will only be counted once for that preferred term. Similarly, if a subject experiences multiple AEs within the same system organ class, that subject will be counted only once in that system organ class. When summarizing AEs by severity, only the most severe occurrence within the preferred term or system organ class will be used. Similarly, when summarizing AEs by relationship to study drug, only the most related occurrence within the preferred term or system organ class will be selected for displays in summary tables.

An overall summary will include, by treatment group and overall, the number and percentage of subjects reporting at least 1 TEAE in the following categories:

- Any TEAE
- Treatment-related TEAE
- Serious TEAE
- TEAE leading to discontinuation of the study drug
- TEAE leading to death.

The following TEAE frequency tables will be prepared summarizing the overall number of TEAEs, the number and percentage of subjects reporting at least one TEAE by MedDRA System Organ Class (SOC) and preferred term (PT), by treatment group and overall:

- All TEAEs
- Serious TEAEs

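### The SAP 5.8 date rule for concomitant medications has no upper limit, so a drug started after the last IPX203 dose can be tabulated as taken with IPX203

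*SAP*

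**What the plan says.** SAP 5.8 gives the definition in two parts. The first states the concept: "Concomitant medications are defined as medications taken while a subject took the open-label study drug". The second, introduced by i.e., is the rule that would be programmed: "medications with stop date on or after the date of the first administration of the open-label study drug or those that are ongoing".

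Records that meet the rule feed a table by ATC class and preferred name. They also feed a second table by anti-PD class (amantadine, selective MAO-B inhibitors, anticholinergics, dopamine agonists, others), with antidepressants and sleep aids alongside. There is no category for drugs begun after treatment. SAP 5.1 uses the same five anti-PD classes to form subject subgroups for the treatment-emergent adverse event (TEAE) tables, and gives no definition of concomitant of its own.

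Other parts of the SAP do set limits. A TEAE must start "on or after the date of the first open-label study drug administration" and "no later than 1 day after the last study drug dose in the study". SAP 3.3 has treatment duration "defined as [the date of last dose] – [the date of first dose] + 1", so a last-dose date is already relied on. The first-dose date is not captured. SAP 2.1 ties it to Visit 1: "It will be assumed that this dose is taken on the day of Visit 1 after all study assessments".

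On collection, Protocol 9.2.1 says "All concomitant medications taken during this study will be recorded". The exit visit in Protocol 8.4 includes the step "Update IPX203 regimen (dose, frequency, number of capsules) and other concomitant medications", and Protocol 8.5 sends early withdrawals through the same exit procedures.

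**The concern.** The concept needs overlap between the medication and IPX203, which takes two conditions: the drug had not ended before IPX203 began, and it had begun before IPX203 ended. The rule contains only the first. A drug started after the last IPX203 dose necessarily has a later stop date or is ongoing, so it always passes.

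Two displays are exposed. The medication tables are where a reader looks to see what was taken alongside IPX203. Protocol 9.2.1 allows apomorphine, supplemental carbidopa and COMT inhibitors to be initiated here although they were barred in the parent study, so new use of them is of interest. A table that mixes drugs added to IPX203 with drugs begun after it blurs that reading. In the SAP 5.1 subgroups, a subject could be classed as taking, say, a dopamine agonist on the strength of one begun only after IPX203 had ended.

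**Working it through.** There is no figure in the plan to reproduce. The check applies the written rule to hypothetical medication records and compares it with a true overlap rule.

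Inputs. Day 1 = Visit 1 = first dose (SAP 2.1 assumption). Last dose on day 100 and exit visit on day 110 are illustrative assumptions; the result depends only on there being a gap between them. SAP relative days have no day 0, so the day before Visit 1 is day −1.

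Rules compared:
- SAP 5.8: stop ≥ day 1, or ongoing.
- Overlap: start ≤ day 100, and (stop ≥ day 1, or ongoing).
- Strict: start ≤ day 100, and (stop > day 1, or ongoing).

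| Record | SAP 5.8 | Overlap | Strict |
|---|---|---|---|
| Stopped day −1 | no | no | no |
| Stopped on the Visit 1 date | yes | yes | no |
| Stopped day 2 | yes | yes | yes |
| Begun before the study, ongoing | yes | yes | yes |
| Days 30 to 60 | yes | yes | yes |
| Started day 100, ongoing | yes | yes | yes |
| Started day 101, ongoing at exit | **yes** | no | no |
| Days 102 to 106 | **yes** | no | no |

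The SAP rule and the overlap rule differ on the last two records only. Both began after IPX203 ended, so both contradict the concept in SAP 5.8. Adding the start-date condition removes them and leaves the other six unchanged.

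Consequence for SAP 5.1. The earliest start for a wrongly counted drug is 100 + 1 = day 101. The latest onset for a fully dated TEAE is also 100 + 1 = day 101. Such an event therefore began before the drug that defines the subgroup or, at the latest, on the same calendar day. It cannot have begun on a later day.

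Lower end. The strict rule differs from the overlap rule on one record only, the drug stopped on the Visit 1 date. Dates alone cannot show whether its final intake came before or after the first IPX203 dose.

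**The case against.** The best defence is that SAP 5.8 opens with the correct concept, so the intended limit is on the page and the date rule is only an incomplete paraphrase. That stands as evidence of intent. It does not settle what would be programmed, because the explicit date condition is the part that translates into code, and SAP 5.1 shows that this SAP writes an upper limit when it wants one.

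The defence is also right that exposure is narrow. The protocol schedules no visit after Visit 4, and unused drug is collected there, so completers should have little or no gap between last dose and exit. Replacement levodopa or a COMT inhibitor would fall under the others class and be shown by preferred name, leaving the four named anti-PD classes untouched. A drug from a named class, such as a dopamine agonist, would still move a subject into a named subgroup. No test, clinical utility score, exposure summary or TEAE definition changes.

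Three stronger readings are tempting and are not supported:
- *Drugs ended before the first dose are counted too.* Any stop date before Visit 1 is excluded. Only a stop date equal to Visit 1 qualifies. SAP 2.1 places the first dose after the study assessments but says nothing about when other drugs were taken that day. Same-day inclusion also matches the TEAE convention.
- *The error concentrates in subjects in whom IPX203 failed.* Protocol 7.3 lists nine reasons for discontinuation, of which lack of efficacy is one.
- *A sizeable share of subjects is misclassified.* With 15% to 25% withdrawal from about 300 enrolled and one third to one half starting a new drug before exit, the count would run from 0.15 × 300 × 1/3 = 15 to 0.25 × 300 × 1/2 = 37.5. Neither rate appears in the documents, so that range should carry no weight.

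**Conclusion.** The concern holds at the upper end only. The date rule in SAP 5.8 does not implement the definition it follows: a medication started after the last IPX203 dose but recorded by Visit 4/early termination can be tabulated as concomitant, and can place the subject in a SAP 5.1 subgroup. This rests on two readings: that the explicit date rule is what gets programmed, and that SAP 5.1 uses the SAP 5.8 meaning of concomitant, since it states no other.

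Severity is minor. The effect is confined to descriptive medication tables and TEAE subgroup membership, and arises mainly in early withdrawals with a gap between last dose and exit visit. The documents give neither the length of that gap nor how often a new drug is begun in it, so the number of subjects affected is unknown.

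**What to change.** Add to the SAP 5.8 rule: *and start date on or before the date of the last open-label dose; a missing or partial start date is treated as concomitant unless the known parts rule this out.* The partial-date handling follows the approach that SAP 5.1 already takes for adverse events.

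List drugs started after the last dose separately as post-treatment medications. State that the SAP 5.1 medication subgroups use this definition. Use the same last-dose date as in SAP 3.3 and 5.1.

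Keep the inclusion of drugs with a stop date on the Visit 1 date, and state it as a convention. Requiring a later stop date would drop a drug last taken that day after the first IPX203 dose, and would break alignment with the TEAE rule.

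The cost is one sentence in the SAP, one date condition in the program and one extra listing. No new data collection is needed.

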9 APPENDICES

9.1 Schedule of events

Table 1 Schedule of Events

| | Visit 1 Baseline | 9 Months of IPX203 Therapy | | | | |
|---|---------------------|---|------------|---|------------|---|
| | | Study Drug Resupply Months 1- 2 | Visit 2 | Study Drug Resupply Months 4- 5 | Visit 3 | Study Drug Resupply Months 7- 8 |
| Study Month | 0 | | 3 | | 6 | |
| ICF and HIPAA Authorization ^b | X | | | | | |
| Check Inclusion/Exclusion Criteria | X | | | | | |
| Update Medical History | X | | | | | |
| Physical Examination | X | | | | | X |
| Vital Signs ^c | X | | X | | X | X |
| Weight | X | | X | | X | X |
| C-SSRS ^d | X | | X | | X | X |
| Clinical Laboratory Tests ^e | X | | X | | X | X |
| Urine Pregnancy Test | X ^f | | | | | |
| ECG | X | | X | | X | X |
| MDS-UPDRS Parts I-IV ^g | X | | X | | X | X |
| PGI-S ^h | X | | X | | X | X |
| CGI-S ⁱ | X | | X | | X | X |
| PDQ-39 ^j | X | | X | | X | X |
| GCSI ^k | X | | | | | X |
| NMSS ^l | X | | X | | X | X |
| PDSS-2 ^m | X | | X | | X | X |
| PAS ⁿ | X | | X | | X | X |
| TSA ^o | | | X | | X | X |
| ZBI-12 ^p | X | | X | | X | X |
| EMSQ ^q | X | | X | | X | X |
| Contact phone calls ^r | | | X | | X | X |
| Contact IWRS to dispense study medication | X | X | X | X | X | X |
| Collect empty medication bottles and any unused study drug/Perform study drug accountability | | X | X | X | X | X |
| Adverse Events | X | | X | | X | X |
| Concomitant Medications | X | | X | | X | X |

^a Visit 1 is expected to occur on the same day as the End-of-Study Visit (Visit 7) of Study IPX203-B16-02 but not later than 1 week. After the subject provides consent for this study, carry over and record information from procedures at the End-of-Study Visit of IPX203-B16-02 as the Baseline data for this study.

^b Subjects enrolled at sites in the United States (US) must sign HIPAA authorization prior to the conduct of any study-specific procedures.

^c Record vital signs (blood pressure, heart rate, respiratory rate, and temperature [Visit 1 and Study Exit

only]) after subject has been resting supine for at least 5 minutes, then record orthostatic blood pressure and heart rate after subject has been standing for approximately 2 minutes.

^d See Appendix B of the protocol.

^e See Appendix C of the protocol.

^f This test will be performed at Visit 1 of this study.

^g See Appendix D of the protocol.

^h See Appendix E of the protocol.

ⁱ See Appendix F of the protocol.

^j See Appendix G of the protocol.

^k See Appendix H of the protocol.

^l See Appendix I of the protocol.

^m See Appendix J of the protocol.

ⁿ See Appendix K of the protocol.

^o See Appendix L of the protocol.

^p See Appendix M of the protocol.

^q See Appendix N of the protocol.

^r Contact phone calls for Visits 2 through 4:

- Following Visit 1, contact subjects weekly for the first month and then monthly thereafter between visits to review the subject's medication dosing regimen.
- Instruct subjects to call the study site before making any changes to their IPX203 dosing regimen.
- Update and record concomitant medications and IPX203 dose adjustments.
- Contact subjects 1 day prior to Visits 2 to 4 to remind them to bring back any unused medication and empty medication bottles.

CGI-S = Clinical Global Impression of Severity Scale; C-SSRS = Columbia-Suicide Severity Rating Scale; ECG = electrocardiogram; EMSQ = Early Morning Symptoms Questionnaire; GCSI = Gastroparesis Cardinal Symptom Index; HIPAA = Health Insurance Portability and Accountability Act; ICF = informed consent form; IWRS = interactive web response system; PAS = Parkinson Anxiety Scale; PD = Parkinson's disease; PDQ-39 = 39-Item Parkinson's Disease Questionnaire; PDSS-2 = Parkinson's Disease Sleep Scale-2; PGI-S = Patient Global Impression of Severity Scale; MDS-UPDRS = MDS version of Unified Parkinson's Disease Rating Scale; NMSS = Non-Motor Symptom Assessment Scale; TSA = Treatment Satisfaction Assessment; ZBI-12 = 12-Item Zarit Burden Interview
